### **13. Recruitment Methods**

Once the ECC-VRC staff learn of a potential participant, they may contact the patient's physician to determine whether the patient is suitable for participation in a research study. The study staff may contact the potential participant and the LAR to determine their interest in participating in the study. The staff may learn of potential participants either by reviewing test results in the medical records (for example, a positive diagnostic test) or from physician colleagues.

In the case of hospitalized patients, the patients' physician must be willing to act as the liaison between the patient, the patient's LAR and the research team. For outpatients, the primary physician may be asked to serve as the contact person for the patient. If the patient is ambulatory and has recovered from the illness, such patients may be asked to visit the ECC-VRC if they are interested in participating in the study. There will be no monetary incentive for the patient's physicians to refer patients to this study.

In the case of healthy volunteers, ECC staff will utilize the adult participant database for those who agreed to be contacted for future studies.

Research staff will utilize the Emory IRB approved Oral Consent form to prescreen interested participants. If the subject/LAR provides oral consent, the research staff will proceed with a prescreening telephone questionnaire to exchange relevant study information with the subject. Research staff will collect the participant's name, phone number, email, age, COVID history, respiratory history and medical history and offer time for questions and study information. If the subject/LAR is interested in participation, the first clinic visit will be made at which time full written consent or full oral consent (as stated in the consent section of this document) will be obtained prior to the initiation of any research activities.

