### 6. Procedures Involved:

Patients seen at Emory COVID-19 testing centers will be asked to participate in the study. Those who consent to participate will have a cough specimen collected over the following 24 hours and their medical record will be reviewed for age, sex, race/ethnicity, underlying medical conditions, their SARS-CoV-2 PCR test results, and other diagnostic test results if being seen for a COVID exposure or illness or other acute respiratory illness. The patient will be given the PneumoniaCheck device with a sterile ziplock bag and cooler with cold packs to keep the device, shown a video, given verbal guidance for collecting the first set of coughed specimens, and asked to do 4 additional sets of 10 coughs into the same device. The device will be stored in the ziplock bag in a cooler between collections. After the specimen is collected, the specimen will be collected by study personnel and transported using standard operating procedures for specimen transportation to the laboratory. In the laboratory, in a BSL2 biosafety cabinet with BSL2+ conditions, the PneumoniaCheck will be double bagged for storage at -80°C. Later the specimen is processed and tested for SARS-CoV-2 RNA by real time PCR and biomarkers by a multiplex Luminex assay and mass spectrometry. Each specimen will be given an identification number, without personal identifying information, which will be used to link laboratory results to clinical and epidemiologic data.

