### **10. Inclusion and Exclusion Criteria**

We will enroll up to 75 adult SARS-CoV-2 PCR positive patients and up to 30 adult patients with a non-COVID-19 acute respiratory illness being treated either as inpatients or outpatients to participate in the study. We will also enroll up to 30 adult healthy controls. We will collect coughed specimens during 5 sessions of 10 or more coughs separated by at least 15 minutes. Patients who consent to participate in the study will be instructed on method of collection and asked to collect 5 sets of 10 cough specimens over the next 24 hours with the same PneumoniaCheck device. After specimen collection is completed, the device is transferred to the laboratory and stored for processing. For processing, the filter (see **Figure 1**) with the captured coughed droplets is removed from the device, captured droplets eluted from the filter, and the eluate and filter are stored at -80°C for later testing, PCR for SARS-CoV-2 RNA, multiplex Luminex and Simoa Quanterix system assays for biomarkers of inflammation, enzyme immunoassay (EIA) for surfactant A, and an enzymatic assay for amylase. The PCR results, positivity and CT values, in

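### The protocol lets recovered patients be invited and sets no maximum time from positive PCR to cough, so cleared virus can be scored as a device miss in the primary sensitivity

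*Protocol*

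**What the plan says.** **Who may be invited.** Section 13 lets staff find candidates through the chart: "The staff may learn of potential participants either by reviewing test results in the medical records (for example, a positive diagnostic test"), or through physician colleagues. It then says: "If the patient is ambulatory and has recovered from the illness, such patients may be asked to visit the ECC-VRC", on condition that they are interested in taking part. The illness is not named.

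**Who is in the COVID-19 group.** Section 10 says: "We will enroll up to 75 adult SARS-CoV-2 PCR positive patients". It gives no date for that test. The words "being treated either as inpatients or outpatients to participate in the study" follow the mention of the non-COVID-19 group, and they can be read as covering that group alone or both patient groups.

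**Where and when.** Section 6 says: "Patients seen at Emory COVID-19 testing centers will be asked to participate in the study". On timing it says: "Those who consent to participate will have a cough specimen collected over the following 24 hours". That clock starts at consent. Section 9 repeats it and also allows further samples later, with no window.

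**The reference result.** Section 6 takes it from the medical record, where staff review "their SARS-CoV-2 PCR test results, and other diagnostic test results if being seen for a COVID exposure or illness". The date of the PCR sample is not among the listed items, and no reference PCR at the time of coughing is described.

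**The scoring rule.** Sections 10 and 17 both equate the cough PCR results in COVID-19 patients with the sensitivity, and those in the other two groups with the specificity. Neither sets a condition on time since the positive test.

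**The concern.** Sensitivity is the proportion positive among people who have the target condition when they are sampled. Here the condition is established by an earlier test found in the record, and the cough may follow at any distance in time. If RNA has gone by then, a negative cough result is correct, yet the stated rule counts it as a miss.

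The primary sensitivity would then depend on how many late or recovered people happened to be recruited as well as on how well the device captures virus. Without the reference sample date, a reader could not separate poor capture from late sampling. Section 4 also names following the course of disease as a possible use of the specimen. Late samples suit that question, but it is not diagnostic sensitivity and does not belong in the same proportion.

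**Working it through.** **Inputs**

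- N = 75, the COVID-19 cap in Section 10. The caps there sum to 75 + 30 + 30 = 135, which matches the total sample size in Section 1. The protocol gives no power or precision calculation to reproduce.
- S = device sensitivity in people still shedding RNA. Not given; assumed, shown as a range.
- k = number of the 75 whose RNA has cleared before the cough. Not given; shown as a range.
- A cleared participant is taken as negative on the cough PCR. This assumption is relaxed in step 4.

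**1. Attenuation.** Expected estimate = S × (75 − k)/75. The relative loss per cleared participant is 1/75 = 1.33%, whatever S is.

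**2. Ceiling for a perfect device (S = 1)**

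| k | Calculation | Highest expected sensitivity |
|---|---|---|
| 1 | 74/75 | 98.7% |
| 5 | 70/75 | 93.3% |
| 10 | 65/75 | 86.7% |
| 15 | 60/75 | 80.0% |

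**3. Absolute loss for S from 70% to 95% (assumed)**

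- Per cleared participant: 0.70/75 = 0.93 points to 0.95/75 = 1.27 points.
- At k = 5: 0.70 × 5/75 = 4.67 points to 0.95 × 5/75 = 6.33 points.

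For comparison with sampling error, take S = 0.90 and k = 15. The expected estimate is 0.90 × 60/75 = 72%, or 54 of 75. The exact (Clopper-Pearson) 95% interval is 60.4% to 81.8%, which excludes the assumed true value of 90%.

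**4. Some recovered people still positive (illustration only).** Assume 85% sensitivity in current infection, 15 recovered among the 75, and 10% to 40% cough positivity after recovery:

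- (60 × 0.85 + 15 × 0.10)/75 = 70.0%
- (60 × 0.85 + 15 × 0.40)/75 = 76.0%

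The loss from 85% is then 9 to 15 points.

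**5. Precision cost of a restricted denominator.** Wilson 95% intervals at an assumed 85%:

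| n | Interval | Half-width (points) |
|---|---|---|
| 75 | 75.2% to 91.4% | 8.06 |
| 70 | 74.8% to 91.5% | 8.35 |
| 60 | 73.9% to 91.9% | 9.01 |

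**The case against.** The strongest reply is that the protocol means current patients. Section 10 governs eligibility, and its reference to treatment as inpatients or outpatients reads naturally as covering both patient groups. Sections 1 and 21 use similar wording, Section 6 recruits at testing centers, and Section 22 sets the research in inpatient or outpatient care. On this view Section 13 only arranges contact and place of visit, and the unnamed illness could be a non-COVID-19 one, which would leave the sensitivity untouched. Section 22 also mentions follow-up visits, which might explain why recovered people would attend.

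Part of this stands. The text is ambiguous, and testing-center recruitment will often mean a recent test. But Section 13 says "such patients may be asked to visit the ECC-VRC if they are interested in participating in the study", which describes first enrolment and not follow-up. Healthy volunteers have their own paragraph there. Chart review and physician referral carry no recency rule. If the treatment wording does cover both groups, it conflicts with Section 13 and still sets no time limit.

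A second reply is that analysis sets and results by time since the test belong in a statistical analysis plan. That is fair for the details of the analysis. Eligibility and the capture of the PCR date are protocol matters, however, and an analysis plan can stratify only by a date that has been recorded.

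A third reply is that the size is hypothetical and that recovered does not mean cleared. Both points are correct, and the figures above are conditional for that reason. Finally, a maximum interval does not exclude clearance within it. That also stands: the change below reduces the problem sharply without removing it.

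**Conclusion.** The concern holds. Followed as written, the recruitment permission and the sensitivity rule together allow a correct negative after clearance to be scored as a device miss, and nothing in the protocol bounds the time between the reference PCR and the cough. The direction is certain: such participants can only lower the primary sensitivity.

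The size cannot be derived from the protocol. It depends on how many people who have cleared RNA are enrolled as COVID-19 patients, and it is zero if there are none. The result rests on two readings: that a recovered person with an earlier positive PCR would be counted in the COVID-19 group, as Section 10's definition allows, and that Section 13 describes enrolment. It should be fixed, with moderate confidence, since the text opens the path to bias but enrolment decides how far it is taken.

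**What to change.** 1. In Sections 10 and 13, state whether recovered COVID-19 patients may be enrolled, and which group the recovery sentence refers to. Reconcile it with the treatment wording in Section 10.
2. In Section 6, add the sample date of the reference PCR to the chart review.
3. In Sections 10 and 17, base the primary sensitivity on COVID-19 participants whose positive reference sample was taken within a pre-stated maximum interval before the first set of coughs, without requiring symptoms. The investigators should choose and justify the interval.
4. Report later or recovered participants separately, as cough PCR positivity by days since the positive reference PCR.

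The cost is some wording and one date from a chart review that is already planned. The downside is a possibly smaller primary denominator: moving from 75 to 60 widens the Wilson half-width by about one point at an assumed 85%, unless the excluded participants are replaced.

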### **14. Withdrawal of Participants**

---

## Detection of SARS-CoV-2 RNA and Biomarkers in Coughed Droplets from Patients with COVID-19 and Controls

Subjects may withdraw from the study at any time by contacting the principle investigator. Subjects may also be withdrawn from the study at the investigators' discretion, for example if the investigator thinks this may affect the subjects' wellbeing. If a subject withdraws, no further data will be collected. If data has been collected, it will not be destroyed.

### **15. Risks to Participants**

The most common risks and discomforts expected in this study are:

- Participants may feel a slight discomfort from coughing repeatedly into the device.

The less common risks and discomforts expected are:

- Loss of confidentiality, all necessary precautions will be in place to reduce breach of confidentiality.

### **16. Potential Benefits to Participants**

Taking part in this research study will not benefit participants personally but the research may help learn new things that may help others in the future.

### **17. Data Management and Confidentiality**

**Data Analysis.** Data will be analyzed based on specimen identification number and group (e.g., COVID-19 patient, non-COVID-19 acute respiratory illness patient, control).

The quality of the specimen captured on the filter, i.e. from the lung or upper respiratory or both will be indicated by surfactant A (lung) and amylase (upper respiratory).

The PCR results will be analyzed as positive or negative and by CT value. The PCR results in COVID-19 patients will indicate the sensitivity of this specimen for detecting SARS-CoV-2 RNA and PCR results in non-COVID-19 patients and controls the specificity. The ratio of surfactant A to amylase indicate lung and upper respiratory contributions to the specimen for all groups. The multiplex Luminex data or Simoa Quanterix system will give biomarkers of inflammation for each group. We will also test some specimens with mass spectrometry to identify novel biomarkers associated with COVID-19 lung disease. Specimens will be saved for additional future research testing.

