### **7. Data and Specimen Banking**

Data will be analyzed based on specimen identification number and group (e.g., COVID-19 patient, non-COVID-19 acute respiratory illness patient, control). Participants will be consented for future contact and use of data and/or specimens. At the completion of this study, we will store any remaining samples for possible future use. The remaining samples may be stored indefinitely and may be used for future studies of genetic causes of the disease. The samples will be stored at Emory Children's Center and Emory Labs.

The sample will be given a unique identification number and stored without participant name or other identifiers. Only the investigator will have a list to know which sample is linked to which patient and this list will be kept confidential in a secure location. If the investigator distributes these samples for research into the causes of the disease, it will be released with the unique identifier, but without any names or medical record numbers.

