### **9. Study Timelines**

Patients who consent to participate in the study will be instructed on method of collection and asked to collect 5 sets of 10 cough specimens over the next 24 hours with the same PneumoniaCheck device. In some cases, participants may be asked to collect additional samples at a later time period.

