### **19. Provisions to Protect the Privacy Interests of Participants**

The privacy of the participants health information is important. As part of this study, we will be consenting the participants prior to the conduct of any research activities . During this process, health care entities who are covered by the Health Insurance Portability and Accountability Act and regulations (HIPAA) will be identified. The participant will be informed that the researchers who obtain IIHI (“individually identifiable health information” or “IIHI”) from the health care entities are not covered by HIPAA. Once they receive the IIHI from the health care entities, they will put it in a separate research record that is not a part of the medical record and that IIHI placed in the separate research record is not be covered by HIPAA.

We will also inform them of their ability to provide research staff consent to access their IIHI for the purpose or research. Data and specimen collection will not be linked to individual participants for privacy interest as described in section 7.

Participants are informed that they do not have to sign the consent form. If they do not sign this consent form, then they may not participate in the research study.

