## **22. Setting**

The research will be done at Emory Healthcare facilities either as an inpatient or outpatient, and Emory Children's Center for Healthy Volunteers and follow up visits.

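### Does analysing by specimen number, with extra later specimens allowed, let one participant count more than once in sensitivity and specificity?

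*Protocol*

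**What the plan says.** The Data Analysis text in Section 17 opens with "Data will be analyzed based on specimen identification number and group", and Section 7 repeats it. Section 6 explains the number: "Each specimen will be given an identification number, without personal identifying information". The same sentence goes on to say that the number links laboratory results to clinical and epidemiologic data.

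The planned collection is one pooled specimen per person. In Section 9 participants are "asked to collect 5 sets of 10 cough specimens over the next 24 hours with the same PneumoniaCheck device", and Sections 5, 6 and 10 also put all five sets into one device. Section 9 then adds: "In some cases, participants may be asked to collect additional samples at a later time period". Section 22 mentions "follow up visits" without saying what is collected at them.

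Sections 10 and 17 take sensitivity from the PCR results in COVID-19 patients, and specificity from those in non-COVID-19 patients and controls. No section says whether the first, any positive, or every specimen counts for a person with several.

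On linkage, Section 7 says "Only the investigator will have a list to know which sample is linked to which patient", whereas Section 19 says "Data and specimen collection will not be linked to individual participants for privacy interest" and refers back to Section 7.

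**The concern.** The primary aim is an estimate of sensitivity and specificity, so the denominator matters. If the specimen is the unit and some people give two, those people are counted twice, at different points in the illness. Two harms could follow. Results from one person are correlated, so an interval that treats them as independent is too narrow. Later specimens may also be less often positive, which would lower the pooled sensitivity. A rule that counts a person as positive if any specimen is positive would instead raise it. The choice could therefore move the main result either way, and it could be made after the results are seen.

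Two other passages seem to add to the worry. If specimens really could not be linked to people, repeats could not be grouped by person. And Section 13 says "If the patient is ambulatory and has recovered from the illness, such patients may be asked to visit the ECC-VRC", so even a first specimen might be taken late.

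**Working it through.** **No figure to reproduce.** The protocol gives no expected sensitivity, interval method, precision target or number of repeat specimens. Only the cohort sizes in Section 10 come from the document: up to 75 COVID-19 patients, 30 with other acute respiratory illness and 30 healthy controls. Every other input below is an assumption.

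**One specimen per person.** The denominators are up to 75 for sensitivity and up to 30 + 30 = 60 for specificity. If 60 of 75 were positive, sensitivity would be 0.80 (exact 95% interval 0.692 to 0.884).

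**Least favourable reading: all specimens pooled as independent.** Let k of the 75 give one extra specimen. Assume first-specimen sensitivity 0.80, later-specimen positivity L from 0.8 to 0.2, and within-person correlation ICC from 0.1 to 0.6.

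- Pooled sensitivity = (60 + k × L) / (75 + k).
- True over nominal standard error = √(1 + 2k × ICC / (75 + k)), with L = 0.80. Example for k = 8, ICC 0.6: √(1 + 9.6/83) = 1.06.
- Coverage: simulation with 200,000 replicates, Wilson 95% interval, L = 0.80.

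| k | Specimens | Pooled sensitivity, L = 0.8 / 0.6 / 0.4 / 0.2 | SE ratio, ICC 0.1 / 0.3 / 0.6 | Coverage (%), ICC 0.1 / 0.3 / 0.6 |
|---|---|---|---|---|
| 0 | 75 | 0.800 | 1.00 | 94.1 |
| 8 (about 10%) | 83 | 0.800 / 0.781 / 0.761 / 0.742 | 1.01 / 1.03 / 1.06 | 94.4 / 94.0 / 93.3 |
| 19 (about 25%) | 94 | 0.800 / 0.760 / 0.719 / 0.679 | 1.02 / 1.06 / 1.11 | 94.3 / 93.2 / 91.9 |
| 38 (about 50%) | 113 | 0.800 / 0.733 / 0.665 / 0.598 | 1.03 / 1.10 / 1.18 | 93.2 / 91.6 / 88.9 |

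With few repeats the loss of coverage is at most about one percentage point. At ICC 0.1 and k = 8 or 19, coverage is no worse than with no repeats. The large figures need half the cohort to repeat, together with a high correlation or a steep fall in positivity.

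**Any-positive rule.** With L = 0.40 and independent results, sensitivity = (60 + k × 0.2 × 0.4) / 75. This gives 0.82 for k = 19, 0.84 for k = 38 and 0.88 for k = 75.

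**Does the text require pooling?** Three readings bear on this.

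1. The specimen-number sentence stands in the confidentiality and banking sections, and Section 6 presents the number as a coded link to the clinical record. It describes how records are keyed at least as naturally as it sets a unit of analysis.
2. The groups it names are groups of people, and the following text in Section 17 defines sensitivity and specificity by results in those people.
3. Extra samples are foreseen only in some cases, and no section assigns them to the primary aim. Section 4 mentions following the course of disease as a possible use of coughed specimens, which would be a natural separate purpose, though the protocol does not assign it.

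**Linkage.** Section 19 cites Section 7, and Section 7 describes coded storage with a list held by the investigator. Read together, they describe de-identified data with a retained key, loosely worded in Section 19. Repeats can be grouped by person.

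**Recovered patients.** Late first specimens would affect sensitivity even with exactly one specimen each. That is a separate question of recruitment and timing, which a rule for choosing among repeats would not settle.

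**The case for a change.** The strongest contrary argument is that the protocol is not silent. It names the specimen number as the basis of analysis and, separately, allows repeats. On that view the point is badly fixed rather than left open, and an analysis plan that used the participant as the unit would depart from the literal wording. The remedy would also be cheap: a few sentences naming the first specimen.

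Part of this stands. The wording does not make plain that the participant is the unit, and no section supplies the missing rule. The bias could also exceed the loss of coverage: with 8 repeaters and later positivity of 20%, pooled sensitivity falls by 5.8 points (80.0 to 74.2).

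But that shift occurs only if an analyst pools early and late specimens as separate subjects, which the protocol does not direct. The literal reading depends on taking a record-keeping sentence as a statistical rule, against the patient-based definitions that follow it. Without that reading, what remains is an unstated detail of the kind normally settled in an analysis plan. Only the protocol was available here, so its absence from the protocol is not a defect.

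**Conclusion.** No change to the plan is called for. The protocol leaves open which specimen counts for the few participants who may give more than one. It does not fix a wrong unit, and the planned collection gives each participant one specimen. An analyst would take the specimen from the first 24-hour device for the primary estimates and report later ones separately or with clustering on participant. The retained sample-to-patient list makes that possible.

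No bias or loss of coverage can be shown from the documents. On assumed inputs, pooling with about 10% repeating would cost at most about one percentage point of coverage and between 0 and 5.8 points of sensitivity. With one specimen per person both are zero. This conclusion rests on repeats being occasional, as Section 9 suggests, and on participant-level handling at analysis. If a large share of the COVID-19 cohort gave later specimens and these were pooled, the effect would not be small. The linkage wording in Section 19 is loose but changes no result, and the recovered-patient question is separate.

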## Detection of SARS-CoV-2 RNA and Biomarkers in Coughed Droplets from Patients with COVID-19 and Controls

### 1. Study Summary

Study Title	Detection of SARS-CoV-2 RNA and Biomarkers in Coughed Droplets from Patients with COVID-19 and Controls
Study Design	Single Center comparative trial with controls
Primary Objective	Determine the sensitivity and specificity of detecting SARS-CoV-2 RNA in cough-generated droplets captured with the PneumoCheck™
Secondary Objective(s)	Determine the value of detecting inflammatory cytokines and chemokines and other biomarkers in cough-generated droplets with PneumoniaCheck in evaluating disease in COVID-19 patients.
Research Intervention(s)/Interactions	Determine the value of PneumoniaCheck specimens for diagnosing SARS-CoV-2 infection and assessing disease state and understanding pathogenesis of disease.
Study Population	We will enroll up to 30 SARS-CoV-2 PCR positive patients and up to 30 patients with a non-COVID-19 acute respiratory illness being treated either as inpatients or outpatients to participate in the study. We will also enroll up to 30 healthy controls.
Sample Size	Up to 135 across all cohorts
Study Duration for individual participants	Those who consent to participate will have a cough specimen collected over the following 24 hours and asked to do 4 additional sets of 10 coughs into the same device
Study Specific Abbreviations/ Definitions	NA
Funding Source (if any)	Internal funding in addition to Georgia Tech grant

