### 2. Objectives

Goal: Determine the value of PneumoniaCheck specimens for diagnosing SARS-CoV-2 infection and assessing disease state and understanding pathogenesis of disease.

Aim 1: Determine the sensitivity and specificity of detecting SARS-CoV-2 RNA in cough-generated droplets captured with the PneumoCheck™

Aim 2: Determine the value of detecting inflammatory cytokines and chemokines and other biomarkers in cough-generated droplets with PneumoniaCheck in evaluating disease in COVID-19 patients.

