## **Detection of SARS-CoV-2 RNA and Biomarkers in Coughed Droplets from Patients with COVID-19 and Controls**

---

COVID-19 patients will indicate the sensitivity of this specimen for detecting SARS-CoV-2 RNA and in non-COVID-19 patients and controls the specificity. The ratio of surfactant A to amylase indicate lung and upper respiratory contributions to the specimen for all groups. The multiplex Luminex and Simoa Quanterix system data will give biomarkers of inflammation for each group and differences between groups biomarkers associated with COVID-19. We will also test some specimens with mass spectrometry to identify novel biomarkers associated with COVID-19 lung disease.

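### Sections 10 and 17 draw one specificity from ill patients and healthy volunteers; no specificity for the ill group is fixed, and a combined figure would depend on the enrolment mix

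*Protocol*

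**What the plan says.** The primary objective (Sections 1 and 2) is "Determine the sensitivity and specificity of detecting SARS-CoV-2 RNA in cough-generated droplets captured with the PneumoCheck™". The overall goal in Section 2 begins "Determine the value of PneumoniaCheck specimens for diagnosing SARS-CoV-2 infection" and goes on to disease state and pathogenesis.

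Two places say where specificity comes from. Section 17, Data Analysis, has sensitivity shown by the PCR results in COVID-19 patients and continues "PCR results in non-COVID-19 patients and controls the specificity". Section 10 has the same rule: "in non-COVID-19 patients and controls the specificity". Neither gives a separate specificity for the patients with acute respiratory illness or names a primary negative group.

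Section 17 opens with a more general sentence: "Data will be analyzed based on specimen identification number and group (e.g., COVID-19 patient, non-COVID-19 acute respiratory illness patient, control"). Ill non-COVID-19 patients and controls are therefore listed there as separate groups.

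On numbers, Section 10 says "We will enroll up to 75 adult SARS-CoV-2 PCR positive patients and up to 30 adult patients with a non-COVID-19 acute respiratory illness" and "We will also enroll up to 30 adult healthy controls". Section 13 says that the healthy volunteers come from a database of adults who agreed to be contacted for future studies.

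**The concern.** The rule names two quite different negative groups in one clause and gives them a single specificity. Elsewhere the same text says so when it wants results by group: the surfactant-to-amylase ratio is given for all groups and the inflammation markers for each group, and Section 10 adds differences between groups. Specificity carries no such qualifier, so an analyst following the text would most naturally produce one figure over both groups.

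For a diagnostic purpose the two groups answer different questions. Ill patients without COVID-19 show whether the specimen separates COVID-19 from other respiratory illness. Database volunteers are not presenting for diagnosis. Two things are at stake if the groups are combined:

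- Each group is capped but has no minimum and no fixed ratio. Whenever specificity differs between the groups, the combined figure moves with the enrolment mix while device performance stays the same.
- The interval is narrower than the ill group alone can support, because up to half of the denominator comes from volunteers.

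**Working it through.** **Inputs.** Section 10: up to 30 ill non-COVID-19 patients and up to 30 healthy controls. Section 1: "Up to 135 across all cohorts". The caps in Section 10 reproduce that total: 75 + 30 + 30 = 135. (Section 1 also still gives 30 COVID-19 patients, and Section 12 gives 90 participants in all; neither changes the 30 + 30 negatives.) The protocol states no specificity target, precision, power or false-positive rate, so there is no specificity figure to reproduce, and the rates below are assumptions shown over a range.

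**Share of volunteers.** At full enrolment, 30/(30 + 30) = 50% of the specificity denominator.

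**Combined specificity.** Sp = (n_ill × Sp_ill + n_healthy × Sp_healthy)/(n_ill + n_healthy). Intervals are exact (Clopper-Pearson): for x negatives out of n, the lower limit is the 2.5% quantile of Beta(x, n − x + 1) and the upper limit is the 97.5% quantile of Beta(x + 1, n − x). When x = n, the lower limit is 0.025^(1/n) and the upper limit is 100%.

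**Case A: all false positives in the ill group (30 ill, 30 healthy).**

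| False positives | Ill group, n = 30 (95% CI) | Combined, n = 60 (95% CI) |
|---|---|---|
| 0 | 100% (88.4 to 100) | 100% (94.0 to 100) |
| 1 | 96.7% (82.8 to 99.9) | 98.3% (91.1 to 100.0) |
| 3 | 90.0% (73.5 to 97.9) | 95.0% (86.1 to 99.0) |
| 6 | 80.0% (61.4 to 92.3) | 90.0% (79.5 to 96.2) |

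The combined false-positive rate is 30/60, or half, of the rate in ill patients. If healthy specificity is 99% rather than 100%, an ill-group specificity of 90% gives (90 + 99)/2 = 94.5%.

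**Case B: equal rates.** Three false positives in each group give 27/30 = 90.0% (73.5 to 97.9) in the ill group and 54/60 = 90.0% (79.5 to 96.2) combined. The point estimate is unbiased; only the interval narrows.

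**Case C: false positives only in volunteers.** None in 30 ill and three in 30 healthy give 100% (88.4 to 100) in the ill group and 57/60 = 95.0% (86.1 to 99.0) combined. Here combining understates specificity in ill patients.

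**Dependence on the mix.** Take Sp_ill = 90%, Sp_healthy = 100% and 30 volunteers:

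- 30 ill: (27 + 30)/60 = 95.0%
- 20 ill: (18 + 30)/50 = 96.0%
- 15 ill: (13.5 + 30)/45 = 96.7%
- 10 ill: (9 + 30)/40 = 97.5%

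**The case against.** The strongest reply is that the protocol contains no pooling rule. Sections 10 and 17 name the groups that inform specificity; they set no estimator or denominator, and no word for pooling or combining appears. The first sentence of Section 17 divides the data by group and lists the two negative groups separately. A statistical analysis plan, not available here, may settle the matter. This stands to the extent that combining is the natural reading but not the only one. A reader might infer that the protocol explicitly prescribes one pooled estimate; the text does not go that far.

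A reader might also infer that the reported specificity will be too high because healthy volunteers are easy negatives. The documents do not support that as fact. They give no false-positive rate in either group, equal rates produce no bias, and the reverse is possible: the protocol describes no reference PCR for healthy controls, and an unrecognised infection among them would count as a false positive. Nor does a lower chance of infection among volunteers help the argument, since specificity is conditional on being uninfected.

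Finally, Section 6 also mentions people seen after a COVID-19 exposure, so ill patients are not the whole population in which the specimen might be used. That is correct, but someone attending a testing center after an exposure is not a database volunteer either, so it does not justify letting volunteers form up to half of the denominator.

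The objection does not remove the ambiguity in half of the primary aim, and it does not supply a committed estimate for the ill group.

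**Conclusion.** The point holds in conditional form. The protocol assigns one specificity to two negative groups, fixes none for the ill group, and reads most naturally as a combined figure. If the groups are combined and false positives are commoner in ill patients, the result can overstate specificity for diagnosis: at 30 per group with no false positives in volunteers, the false-positive rate is halved (90.0% reads as 95.0%), and fewer ill patients make the gap larger. Both conditions are assumptions.

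The precision point needs only that the groups are combined. With no false positives at all, the reported lower limit would be 94.0%, while 30 ill patients alone support 88.4%.

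It would go too far to say that the protocol explicitly orders pooling or that its specificity will be inflated. The clarification is worth making because it concerns the primary aim and costs almost nothing.

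**What to change.** In Sections 10 and 17, state that specificity is estimated separately in the patients with non-COVID-19 acute respiratory illness (primary) and in the healthy controls, each with an exact 95% confidence interval, and that any combined figure is secondary. If the analysis plan already says this, bring the two protocol sections into line with it.

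The change is one sentence in each section. It needs no additional participants, specimens or assays, and it agrees with the by-group sentence that opens Section 17. The downside is a wider and possibly lower headline specificity.
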